13.5 Sample Size

13.5.1 The primary aim of this study is to evaluate influence of the partner vs. survivor-only exercise intervention on psychological distress in cancer survivors, as measured by the POMS total score at the post-treatment assessment. Based on previous research on EXCAP[®] that we have conducted, and assuming a SD of 13.01 for the POMS total score and a correlation of 0.7 between baseline and post-treatment, we will have 80% power to detect difference of 6.90 (a moderate effect size of 0.58) between the two groups at the 0.05 level. The power curve in Figure 5 shows the statistical power we have to detect difference between the two treatment arms in changes from baseline to post treatment on the POMS total score should the proposed study yield smaller mean differences.

Figure 5: Model Power Curve

Please confirm that the patient has no physical limitations (e.g., cardiorespiratory, orthopedic, central nervous system) that contraindicate participation in maximal physiological fitness testing, and that you approve their participation in this fitness testing and a low to moderate intensity home-based walking and progressive resistance exercise program. Please also note there will only be an exercise physiologist present for this fitness testing, unless on review of the patient's medical history we feel that the presence of a physician (or their designee) is needed.

☐ **YES**, this patient is physically and medically able to participate in maximal physiological fitness testing and a low to moderate home-based walking and progressive resistance exercise program.

Physician (or physician's designee) Approval: _____

Date: _____

Thank you!

[name], MPH
Assistant Professor
University of Rochester School of Medicine and Dentistry
James P. Wilmot Cancer Institute
Department of Surgery

Wilmot Cancer Institute
Department of Surgery
URCC NCORP Research Base
Cancer Control Research Program

UR
MEDICINE

WILMOT
CANCER INSTITUTE

MEDICINE *of* THE HIGHEST ORDER

CAREGIVER ELIGIBLE FOR STUDY

Your patient, _____, is eligible for the study: **Exercise Intervention for Cancer Survivors** (PI: [name]).

Your patient would like to participate in a study being conducted at the James P. Wilmot Cancer Institute of the University of Rochester. This study is being conducted by [name], a clinical investigator in the Department of Surgery. This intervention is designed to see whether exercise can improve the health and well-being of cancer survivors and the health of their caregivers. Your patient was a caregiver to an individual treated for cancer.

Please confirm that the patient has no physical limitations (e.g., cardiorespiratory, orthopedic, central nervous system) that contraindicate participation in maximal physiological fitness testing, and that you approve their participation in this fitness testing and a low to moderate intensity home-based walking and progressive resistance exercise program. Please also note there will only be an exercise physiologist present for this fitness testing, unless on review of the patient's medical history we feel that the presence of a physician (or their designee) is needed.

☐ **YES**, this patient is physically and medically able to participate in maximal physiological fitness testing and a low to moderate home-based walking and progressive resistance exercise program.

Physician (or physician's designee) Approval: _____

Date: _____

Thank you!

[name], MPH
Assistant Professor
University of Rochester School of Medicine and Dentistry
James P. Wilmot Cancer Institute

Wilmot Cancer Institute
Department of Surgery
URCC NCORP Research Base
Cancer Control Research Program

MEDICINE *of* THE HIGHEST ORDER

Department of Surgery

Intervention Protocols

Description of Standardized EXCAP[®] Intervention Clinical Protocol Components

As noted above, each study participant randomized to either the EXCAP-PA or the EXCAP[®] condition is provided with an EXCAP[®] Exercise Kit, which includes a pedometer, resistance bands, two assist strap handles, a written manual, and a carrying bag.

The EXCAP[®] program was designed by an Exercise Scientist certified by the American College of Sports Medicine (ACSM) and is in accordance with the guidelines for exercise testing and prescription as set forth by the ACSM. The prescription is also guided by the “ACSM Exercise Guidelines for Cancer Patients and Survivors.”

The EXCAP[®] Walking Prescription will be based on a patient’s baseline pedometer assessment. Patients will be encouraged to increase their total steps walked each day by a minimum of 5% and a maximum of 20% each week, while maintaining a moderate intensity, during the 8-week intervention period. Patients will also be encouraged to continue increasing their steps and walking during the 3 months post-intervention. [Note: Walking intensity will be monitored via the Rating of Perceived Exertion (RPE) Scale, which is a visual analog scale ranging from 1 = no exertion to 10 = very strong exertion; this is part of the daily diary that participants will keep.]

The EXCAP[®] Progressive Resistance Prescription will be based on a patient’s optimal level of challenge. Patients will be instructed on the proper use of resistance bands. Patients will then be instructed to choose a resistance band with which they can perform 8-12 repetitions of 5 upper body resistance exercises and 5 lower body resistance exercises listed below. Patients will be instructed to begin with 1 set of 8-25 repetitions at a moderately challenging level (RPE 5-8) three days a week. Patients will be instructed to progressively increase to a minimum of 3 and a maximum of 4 sets for each exercise up to seven times per week. (Note. Patients will be instructed in the proper methods for performing each exercise).

The program consists of an initial 45-60 minute meeting with a certified exercise specialist. Participants will be shown the proper methods for performing the exercises and given a prescription for both walking and progressive resistance. A member of the study team will then follow up with weekly phone calls to the participants to check in on their progress, answer any questions, troubleshoot barriers and encourage patients to adhere to the exercise prescription. Our previous study provided the intervention over 4-6 weeks with excellent adherence and no adverse incidents.

Caregivers randomized to the survivor-only EXCAP[®] condition will be instructed not to change their exercise behavior in any way.

A detailed list of the EXCAP[®] exercises is provided below.

Aerobic (Progressive Walking)

Weekly increase in walking

Anaerobic (Progressive Resistance)

Squat

Side Bends

Leg Extension

Leg Curl

Toe Raises

Overhead Press

Biceps Curl

Triceps Extension

Chest Press

Rows

Core strength (crunches, planks)

Description of the EXCAP-PA Dyadic Framework Components

As noted above, survivors and caregivers randomized to the EXCAP-PA intervention arm will each receive EXCAP[®] materials and be instructed in their use together.

The EXCAP-PA dyadic framework was developed by a clinical psychologist ([name]) with a training background in dyadic behavioral interventions. This framework uses clinical skills from other dyadic interventions to train caregivers of LGBT cancer survivors in motivational strategies that can be used to help survivors adhere to the exercise program.

The program's three components are **discussion of LGBT specific stress, assessment of barriers, and elicitation of supportive behaviors.**

In **discussing LGBT specific stress**, the interventionist asks the LGBT cancer survivor open ended questions about experiences as a sexual minority individual seeking cancer care. The LGBT survivor will guide the discussion, but the interventionist may ask about how being a sexual minority affected relationships with care providers, unmet needs that arose during care, and how identity shapes experience of survivorship. The caregiver will then be asked to contribute any of their experiences in providing care for the LGBT survivor. Exercise is introduced in this context as a way the dyad can support one another, even in the stress of cancer or the stress of being a sexual minority seeking cancer care.

In **assessing barriers**, the interventionist asks both participants about the barriers that might interfere with their ability to exercise over the next week. Barriers could include daily obligations, physical concerns or symptoms, or emotional or motivational concerns. Both LGBT survivor and caregiver share their anticipated barriers with one another and with the interventionist.

In behavioral activation research, assessing barriers to accomplishing a behavioral goal is a well-validated method of ensuring goal completion.^{93,94} The same technique is used in Motivational Interviewing, to elicit "change talk" and increase motivation to engage in the behavioral change.⁹⁵⁻⁹⁷

In **eliciting supportive behaviors**, the interventionist first turns the focus onto the LGBT cancer survivor, asking what behaviors by the caregiver would help to overcome the aforementioned barriers. Gentle Socratic questioning is used to refine the exact form of and rationale for these behaviors.

The interventionist then checks in with the caregiver, asking what behaviors the caregiver will try over this next week in supporting the LGBT survivor in overcoming barriers to exercise. Again, questioning is used to ensure that the caregiver knows exactly what behaviors would be most helpful. A final check with the LGBT survivor sets the collaborative goal and expectation for the week.

Supportive behavior exchange is a common technique in many dyadic interventions.⁹⁸⁻¹⁰⁰ Typically behavior exchange techniques involve eliciting desired behaviors from each member

of the dyad on a weekly basis; however, in situations where one member of the dyad is a patient and the other a caregiver, supportive behaviors may be specifically directed at the patient from the caregiver.^{101,102} This partner-assisted approach has been used previously in cancer control interventions, as well.¹⁰³⁻¹⁰⁵

In weekly phone calls in the EXCAP-PA condition, the same intervention format is followed, with assessment of barriers followed by elicitation of supportive behaviors. These calls are always made with both the LGBT cancer survivor and the caregiver together to troubleshoot the past week's goal, establish a new goal for the week, and establish supportive behaviors that the caregiver will use.

In the survivor-only EXCAP[®] condition, calls will be made to the LGBT cancer survivor alone and will involve troubleshooting and setting a goal for the next week, without the dyadic support component.

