Assuming an 85% retention rate and an initial sample of 70 survivors, 60 LGBT survivors will complete the study. Because LGBT survivors are the primary unit of analysis, survivors will be invited to return for follow-up assessment even if their caregivers are unavailable. Study interventions will begin on Study Day 0 and continue for 6 weeks (42 days). The exercise intervention, EXCAP[®], is a standardized intervention developed and tested by the research team at University of Rochester Medical Center (URMC). The actual list of exercises, and the framework for the partner-assisted EXCAP-PA, is provided in the Appendix. Each participant will be monitored by an American College of Sports Medicine Certified Exercise PhysiologistSM. Assessments will be made with validated and methodologically sound measures including self-report questionnaires, assays for expression of biological endpoints, weekly diaries, and actigraphy monitoring.

No special classes of participants such as fetuses, neonates, pregnant women, prisoners, institutionalized individuals or other vulnerable populations will be recruited.

Children, as defined by the National Institutes of Health Grants Policy Statement, will not be included, as cancer survivors under 21 years of age are often considered to fall under pediatric care and may have a very different experience of cancer treatment and caregiving than adult (age 21+) cancer survivors.

All data will be gathered at the PEAK Lab and the URMC Cancer Control Unit.

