6.5.1 The Home-Based Walking and Progressive Resistance Exercise Program is designed by an Exercise Scientist certified by the American College of Sports Medicine (ACSM) and is in accordance with the guidelines for exercise testing and prescription as set forth by the ACSM.

6.5.2 The Home-Based Walking and Progressive Resistance Exercise Program will follow the guidelines listed below.

6.5.2.1 The Home-Based Walking Prescription will be based on a participant's (i.e., survivor's or caregiver's) baseline pedometer assessment. Participants will be given a pedometer (or fitness tracker) and encouraged to increase their total steps walked by a minimum of 5% a week during the 6-week intervention while maintaining a moderate intensity. [Note: Walking intensity will be monitored via the Rating of Perceived Exertion (RPE) Scale, which is a visual analog scale ranging from 1 = no exertion at all to 10 = very strong exertion. Participants will be instructed to aim for an RPE of 5-8, consistent with other studies of EXCAP for cancer survivors.] The upper threshold of the walking prescription of the EXCAP program will be 12,000 steps per day.

6.5.2.2 The Home-Based Progressive Resistance Prescription will be based on a participant's baseline isokinetic strength assessment. Participants will be instructed on the proper use of resistance bands. Participants will then be instructed to choose a resistance band with which they can perform 8-12 repetitions of 5 upper body resistance exercises (bicep curl, tricep extension, chest press, rows, and overhead press) and 5 lower body resistance exercises (leg curl, leg extension, squat, toe raises, and side bends), plus core strengthening exercises. Participants will be instructed to begin with 1 set of 8-12 repetitions at a moderate to challenging level (RPE 5-8), up to 7 times per week. Participants will be instructed to progressively increase to 4 sets for each exercise 3 times per week. (Note. Survivors and caregivers in Arm 1 will both be instructed in the proper methods for performing each exercise as a dyad. Cancer survivors in Arm 2 will be instructed in the proper methods for performing each exercise individually.)

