13.3 Data Analysis

- 13.3.1 The primary outcome measure for this study is the cancer survivor's self-reported psychological distress, as assessed by the 30 item Profile of Mood States (POMS) Total score at the post-intervention time point (~6 weeks after baseline). The primary analyses will involve a comparison of EXCAP-PA relative to survivor-only EXCAP[®] using analysis of covariance (ANCOVA). This procedure assesses the statistical significance of the difference in post-intervention mean between the two arms, controlling for baseline score and using intent to treat analyses with 30 evaluable survivors per arm. The comparison of EXCAP-PA to survivor-only EXCAP[®] assumes a null hypothesis of no difference, using a two-sided alpha. We will use ordinary least-squares estimation and F-tests for testing the fixed effects. Primary aim analyses will treat the LGBT cancer survivor as the unit of analysis. The mean difference between groups with associated 95% confidence intervals will be estimated using the appropriate contrasts. This study will establish initial efficacy of the dyadic intervention and provide an initial effect size for the intervention that will inform the development of a larger Phase III trial.
- 13.3.2 Secondary analyses will use standardized procedures developed by [name] and the Rochester Human Immunology Core to measure serum levels of distress-related biological endpoints (serum amyloid A, CRP, cortisol) via ELISAs. The efficacy of EXCAP-PA relative to survivor-only EXCAP[®] in improving markers of HPA axis functioning (cortisol) and early

inflammation (SAA, CRP) will be assessed using three separate ANCOVAs, each controlling for baseline biological marker values, and two ANCOVAs for dyadic support and intervention adherence. Since the secondary aims, relating to immune biomarkers of distress and provision of support within the dyad, are intended to gather preliminary efficacy data for the development of a larger grant submission, the secondary analyses will also examine mean change scores (i.e., baseline assessment subtracted from the post-intervention assessment), standard deviations, and correlations on these variables for the two study arms.

13.3.3 The current study is neither structured nor powered to permit true analysis of mediation.

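### The prescribed EXCAP exercise dose is not uniquely defined: the protocol body and the intervention appendix contradict each other, and no text says which prevails

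*Combined protocol and SAP*

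**What the plan says.** **Length.** Section 4.1 states "Study interventions will begin on Study Day 0 and continue for 6 weeks (42 days"); sections 5.2, 6.4.7 and 6.5.2.1 also give 6 weeks. The walking prescription in the Intervention Protocols appendix gives a weekly increase of "a minimum of 5% and a maximum of 20% each week, while maintaining a moderate intensity, during the 8-week intervention period", and then encourages further step increases for 3 months.

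**Walking.** In section 6.5.2.1 participants are "encouraged to increase their total steps walked by a minimum of 5% a week during the 6-week intervention while maintaining a moderate intensity", with a ceiling of 12,000 steps per day. The appendix has no daily ceiling; its limit is the 20% weekly maximum.

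**Resistance.** Under section 6.5.2.2 participants "begin with 1 set of 8-12 repetitions at a moderate to challenging level (RPE 5-8), up to 7 times per week". Then: "Participants will be instructed to progressively increase to 4 sets for each exercise 3 times per week". Under the appendix they "begin with 1 set of 8-25 repetitions at a moderately challenging level (RPE 5-8) three days a week", and then "progressively increase to a minimum of 3 and a maximum of 4 sets for each exercise up to seven times per week". Section 6.5.2.2 bases the prescription on baseline isokinetic strength; the appendix bases it on the level of challenge that is optimal for the patient. The arm table in section 5.2 gives resistance up to 7 times a week for 6 weeks.

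**Assessment.** Section 13.3.1 measures the primary outcome "at the post-intervention time point (~6 weeks after baseline"). Section 10.2.1.3 sets the second actigraphy window at days 35 to 42.

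**The concern.** Both texts are current, neither is a record of changes, and no statement ranks one over the other. The appendix cannot be set aside as background: it describes the EXCAP components for participants in both arms, and section 4.1 sends the reader to it for the exercise list and the partner framework.

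The protocol calls EXCAP standardized, and section 13.3.1 says the trial will supply an initial effect size for a Phase III trial. That estimate has to attach to a programme that another team could deliver. Staff also contact participants every week to support adherence and need a single prescription to coach to.

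Exposure is a second reason. The expected average age is 67 (section 3.2) and the exercise is done at home. The appendix's own statement about earlier adherence and absence of adverse incidents refers to 4 to 6 weeks of delivery. Section 6.8.5 ends weekly contact after the post-intervention assessment. If that visit stayed at day 42, the last two weeks of an 8-week programme would have no such contact.

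**Working it through.** **The plan's own figure.** The only design calculation is the power statement in section 13.5.1. Inputs: SD 13.01, baseline-to-post correlation 0.7, difference 6.90, two-sided 0.05, and 30 evaluable survivors per arm (section 13.3.1).

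- Residual SD = 13.01 × √(1 − 0.7²) = 9.291
- Standard error = 9.291 × √(2/30) = 2.399
- Noncentrality = 6.90 / 2.399 = 2.88
- Power from the noncentral t with 57 degrees of freedom = 80.7%

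The stated 80% is reproduced. No term in it depends on exercise dose or programme length.

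**Side by side.**

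| Item | Body | Appendix |
|---|---|---|
| Length | 6 weeks, 42 days (4.1, 5.2, 6.4.7, 6.5.2.1) | 8 weeks, then 3 months of encouraged increases |
| Weekly step increase | at least 5%, no maximum | 5% to 20% |
| Daily step ceiling | 12,000 | none stated |
| Resistance, start | 1 set, 8-12 repetitions, up to 7 times a week | 1 set, 8-25 repetitions, 3 days a week |
| Resistance, end | 4 sets, 3 times a week | 3-4 sets, up to 7 times a week |
| Basis of resistance | isokinetic strength test | optimal challenge |

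Two mismatches lie inside one text. The arm table's frequency (5.2) does not match the end point of 3 times a week in 6.5.2.2. The appendix has the band chosen for 8-12 repetitions but lets the first set run to 25.

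**Resistance sets per exercise per week.**

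- Start: body up to 1 × 7 = 7; appendix 1 × 3 = 3.
- End: body 4 × 3 = 12; appendix up to 3 × 7 = 21 or 4 × 7 = 28.
- Largest end ratio: 28 / 12 = 2.33.

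The frequency of seven is a ceiling, so 21 and 28 are upper bounds for 3 and 4 sets, and the 2.3-fold ratio is an upper bound too.

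**Programme length.** Day 42 is 42/42 = 100% of a 6-week programme and 42/56 = 75% of an 8-week one.

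**Steps.** Assume one compounded increase per week and no ceiling.

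- At 5%: 1.05⁶ = 1.34 and 1.05⁸ = 1.48.
- At 20%: 1.20⁶ = 2.99 and 1.20⁸ = 4.30.

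Section 6.5.2.1 sets no weekly maximum, so growth of 20% a week is also allowed there until the ceiling is met. Baseline steps are not given. Over an assumed range of 3,000 to 6,000 a day, growth at 20% reaches 12,000 after ln(4)/ln(1.2) = 7.6 weeks to ln(2)/ln(1.2) = 3.8 weeks. Over part of that range, whether the ceiling applies would matter within the first 6 weeks.

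**The case against.** The best defence is that the conflict is narrower than the table suggests. Six weeks appears throughout the body and matches the endpoint and actigraphy times, while 8 weeks appears once. Some entries overlap: 8-12 repetitions lie within 8-25, 4 sets lie within 3-4, and frequencies stated as ceilings allow a common value. A daily step ceiling and a weekly rate limit are different in kind and could both apply. Both texts give the same effort range and the same rule for choosing a band. Participants also receive a written manual that is not in the documents and may already settle the matter.

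Much of this stands, and it limits the consequences. It does not remove the conflict: the two lengths cannot both be right, and the instructed direction of the frequency progression is opposite.

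A reader might infer more than the documents support:

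- **That the day-42 endpoint is undefined.** It is defined and consistent. It would fall mid-programme only if staff followed the appendix length.
- **That adherence cannot be scored.** Sections 2.3.2 and 13.1.4 measure it as activity by actigraphy, not as a share of the prescription, so it stays computable. Neither version sets an adherence target; that is a separate gap.
- **That the comparison is biased.** Survivors in both arms receive the same EXCAP prescription, so the conflict does not by itself bias the ANCOVA.
- **That physician clearance becomes ambiguous because of the conflict.** The clearance letters state no weeks, sets, repetitions or step limits, so they neither depend on the conflict nor resolve it.
- **That exercise staff work from the appendix, or have delivered different programmes.** The documents say neither.

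**Conclusion.** Wrong as written: an internal inconsistency that should be fixed. The body and the appendix cannot both be followed on programme length or on the direction of the resistance progression. They differ on starting repetitions and on the basis of the resistance prescription, and each step limit is stated in one place only.

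The clearest measure of size is the end-point resistance volume, with the roughly 2.3-fold gap resting on the appendix frequency being taken at its ceiling. The step-growth figures rest on assumed weekly compounding and, for the timing of the ceiling, on assumed baseline steps; they are illustrations of range. The documents do not show which version enrolled dyads received, so the effect on actual delivery is unknown.

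**What to change.** The clinical and exercise leads should reconcile section 5.2, sections 6.5.2.1 and 6.5.2.2, and the walking and resistance prescriptions in the Intervention Protocols appendix. The result should be one programme length, one resistance progression (sets, repetitions, frequency and basis) and one set of step limits, stated identically wherever they appear. They should then:

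- reissue the appendix, and the participant manual if it is affected;
- confirm that the post-intervention visit matches the end of the reconciled programme;
- record, where it can be established, which version each enrolled dyad received.

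The choice belongs to those leads; nothing here favours either version. The cost is a clarification amendment, the reissued material and some retrospective record checking.
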